5.5 Storage and Stability

Favipiravir is a novel nucleic acid (pyrazine molecule) analogue that interferes with viral ribonucleic acid (RNA) replication. Favipiravir is supplied as a light yellow, film-coated tablet for oral administration containing 200 mg favipiravir. Favipiravir tablets are to be kept in a dry area, stored at 15° C to 30° C and shielded from direct light.

5.6 Study Drug Dispensation

Study drug will be provided from IP depot to the research site. The research site study team member will distribute the IP to each enrolled subject. If transportation is needed, the research site study team member will be responsible for transporting of medications to each enrolled subject.

5.7 Expected Side Effects

Favipiravir is considered a safe drug. No treatment related serious adverse events occurred in licensure studies of favipiravir [2]. The most common adverse events observed in clinical trials are gastrointestinal (diarrhea 2.3%; nausea 2.1%). A similar proportion of subjects in the placebo (25.4%) and favipiravir (25.3%) groups experienced at least 1 adverse event. Further, favipiravir is associated with increased uric acid level which are typically asymptomatic and would be expected to be transient with the duration of treatment to be used in this trial.

5.8 Additional Safety Considerations

For the purpose of this trial, the following are exclusion criteria for study drug administration:

- 1) Subject has a history of hypersensitivity to favipiravir
- 2) Known uncompensated hepatic cirrhosis.
- 3) Current use of the following medications, which cannot be discontinued for the duration of the study: pyrazinamide, hydralazine, more than 3000 mg of acetaminophen per day.

The following safety considerations are based on data from individuals taking favipiravir for influenza. They are listed here for reference.

- Phototoxicity: Nonclinical studies have shown mild phototoxicity. One study subject experienced mild photosensitivity (rash) following a tanning bed session. All subjects should avoid excessive exposure to sunlight or artificial ultraviolet light.
- Laboratory Values: Mild to moderate asymptomatic elevations of uric acid and aminotransferase have been observed in healthy volunteers and subjects with influenza [2] treated with favipiravir in clinical studies. The changes have been reversible upon favipiravir discontinuation.
- Mutagenesis: Favipiravir proved mildly positive under some conditions studied in the mammalian chromosomal aberration test and mouse lymphoma assays at high concentrations. Although the potential for genotoxicity at high exposures cannot be ruled out, evidence indicates that this risk is minimal at the exposures planned in this clinical study.
- GI Tract Lesions: In two proof-of-concept studies of orally administered favipiravir against Ebola virus infection in macaques, GI tract lesions were observed that were not consistent with the known natural history of Ebola nor with previous animal and clinical studies of favipiravir. However, evidence suggests that bacterial infections and pre-existing enterocolitis in the treated macaques may have been responsible, and an ongoing risk to subjects may not exist.
- Contraception:

Females of Childbearing Potential

Female subjects who are of childbearing potential must use an acceptable method of contraception starting from screening through to at least 7 days following the last dose of study medication. Acceptable contraceptive methods for female subjects of childbearing potential include one of the following:

1. Abstinence.
2. One of the following methods:
 - Tubal ligation 4 or more weeks prior to randomization
 - Copper-containing intrauterine device (IUD).
 - Condom AND spermicidal foam/gel/film/cream/suppository.
 - Male partner who has had a vasectomy for at least 6 months. Male partners with vasectomies of <6 months are NOT considered protected.
 - Hormonal contraceptives (oral, injected, transdermal or implanted). The subject must remain on the treatment throughout the study and must have been using hormonal contraceptives for an adequate period to ensure effectiveness (3 months prior to randomization or longer).

Females of Non-Childbearing Potential

Female subjects of non-childbearing potential must meet at least one of the following criteria:

1. Postmenopausal females (Not menstruating for at least one year)
2. Females who have a documented hysterectomy and/or bilateral oophorectomy.

All other females will be considered to be of childbearing potential.

Men

Men must meet at least one of the following criteria:

1. Known to be sterile (have azoospermia)
2. Underwent vasectomy
3. Use condom

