Exclusion Criteria	
An individual who meets any of the following criteria will be excluded from participation in this study:
 
 1. O₂ saturation <94% 2. Shortness of breath at rest 3. Heart rate \geq 125 per minute 4. COVID-19 symptoms first presented >5 days prior to randomization 5. Requirement for hospitalization at the time of enrollment 6. Participation in another trial or use of any experimental treatment for COVID-19 7. Treatment with high steroid dose i.e. >30 mg/day prednisolone equivalent (excluding stable chronic treatment) or remdesivir or anyone receiving SARS-CoV-2 monoclonal antibodies within 3 months prior to enrollment 8. Known sepsis or organ dysfunction/ failure 9. Known infection with a respiratory virus other than SARS-CoV2 (e.g. Influenza) or any known bacterial infection (affecting the respiratory system or any other system) 10. Inability to adhere to study requirements 11. For premenopausal women: unwilling or unable to use effective birth control measures 12. Known allergy to favipiravir 13. Known end-stage kidney disease or requiring hemodialysis or continuous ambulatory peritoneal dialysis (CAPD) 14. Known liver impairment greater than Child-Pugh A 15. Psychiatric illness that is not well controlled (defined as stable on a regimen for more than one year). 16. Known elevated uric acid levels in the past year or taking uric acid lowering medications (allopurinol, febuxostat) 17. History of hereditary xanthinuria or history of xanthine urolithiasis. 18. History of gout or actively being treated for gout.

	19. Current use of the following medications, which cannot be discontinued for the duration of the study: pyrazinamide, hydralazine, more than 3000 mg of acetaminophen per day.
Study evaluations	Subjects will be followed for symptoms and signs of infection (until study day 28), adverse events (any AEs: until study day 14, SAEs: until study day 28), and viral shedding (daily from study day 1 to 10).

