6.2 Exclusion Criteria

An individual who meets any of the following criteria will be excluded from participation in this study:

1. O₂ saturation <94%
2. Shortness of breath at rest
3. Heart rate \geq 125 per minute
4. COVID-19 symptoms first presented >5 days prior to randomization
5. Requirement for hospitalization at the time of enrollment
6. Participation in another trial or use of any experimental treatment for COVID-19
7. Treatment with high steroid dose i.e. >30 mg/day prednisolone equivalent (excluding stable chronic treatment) or remdesivir or anyone receiving SARS-CoV-2 monoclonal antibodies within 3 months prior to enrollment
8. Known sepsis or organ dysfunction/ failure
9. Known infection with a respiratory virus other than SARS-CoV2 (e.g. Influenza) or any known bacterial infection (affecting the respiratory system or any other system)
10. Inability to adhere to study requirements
11. For premenopausal women: unwilling or unable to use effective birth control measures
12. Known allergy to favipiravir
13. Known end-stage kidney disease or requiring hemodialysis or continuous ambulatory peritoneal dialysis (CAPD)
14. Known liver impairment greater than Child-Pugh A
15. Psychiatric illness that is not well controlled (defined as stable on a regimen for more than one year).

16. Known elevated uric acid levels in the past year or taking uric acid lowering medications (allopurinol, febuxostat)
17. History of hereditary xanthinuria or history of xanthine urolithiasis.
18. History of gout or actively being treated for gout.
19. Current use of the following medications, which cannot be discontinued for the duration of the study: pyrazinamide, hydralazine, more than 3000 mg of acetaminophen per day.

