7.1.2 Study Vital Signs Measurements and Health Information

- Oral Temperature: will be measured 2 times daily. It will be documented in the subjects' diary. Subjects will be allowed to take temperature lowering medications such as acetaminophen or NSAIDS.
- Heart rate: will be measured once daily and documented by the subject in the subject's diary.
- Oxygen Saturation: will be measured once daily and documented by the subject in the subject's diary. If the O₂ saturation result is 90-93%, the subject will repeat the measurement 2 hours later. If the result is <90%, the subject is instructed to contact the study team. The study team will decide if a recheck in 2 hours is appropriate or the subject needs further medical evaluation).
- Height and weight: Height and weight should be collected at the screening visit. In cases where this has not occurred at the screening visit, the date of collection will be recorded.

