7.5 Concomitant Therapy

Concomitant therapies are any new or existing medications or therapy taken by the subject including:

Drugs, including but not limited to, prescription, over the counter, birth control tablets/patches/hormonal devices, and homeopathic preparations.

- Nondrug therapies, including but not limited to, thermal/laser/radiation procedures, vitamins, herbal medicines/supplements.

During the screening process, information on all concomitant therapies, medications, and procedures will be recorded in the source documents and appropriate Case Report Form (CRF) along with the diagnosis or reason for use. Once the subject receives the first dose of study drug, recording of concomitant therapies will be limited to any new medication or modification of an existing medication taken for treatment of an AE. These therapies will be recorded in the source documents and appropriate CRF along with the diagnosis or reason for use. Those therapies used for the treatment of an adverse event are to be linked to an AE and documentation of the AE must also be completed

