7.5.1 Rescue Medicine

The study site will not supply rescue medication.

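### The 3000 mg/day acetaminophen limit is written for current use at entry and does not clearly reach subjects who start or escalate after Day 1, while section 7.1.2 permits acetaminophen with no maximum

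*Combined protocol and SAP*

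**What the plan says.** The limit appears three times in nearly the same words: exclusion 19 in the synopsis (section 2.1), item 3 of section 5.8 and no. 19 of section 6.2. The condition is "Current use of the following medications, which cannot be discontinued for the duration of the study", and the medications listed are "pyrazinamide, hydralazine, more than 3000 mg of acetaminophen per day". Section 5.8 introduces its list with "the following are exclusion criteria for study drug administration".

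The only text on acetaminophen during the study is in section 7.1.2: "Subjects will be allowed to take temperature lowering medications such as acetaminophen or NSAIDS". No dose is given and section 5.8 is not cross-referenced.

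Section 7.5 (Concomitant Therapy) lists no restricted or dose-limited medication. It says that after the first dose "recording of concomitant therapies will be limited to any new medication or modification of an existing medication taken for treatment of an AE". Section 9.2.2 asks subjects to report, and site staff to assess, concomitant medication daily during dosing, non-prescription products included. The Schedule of Activities has matching rows.

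**The concern.** A subject can begin the trial with little or no acetaminophen, take more as symptoms continue, and exceed 3000 mg/day while on study drug. That intake is one the protocol itself treats as a reason not to give study drug. The situation is foreseeable. Entry requires at least two symptoms scored 2 or higher, from a list that includes feeling feverish, headache and body aches, and 7.1.2 expressly allows acetaminophen.

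What is at stake is whether a safety threshold set by the sponsor applies while the drug is being taken. The protocol does not say why 3000 mg was chosen, so no mechanism is inferred here.

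**Working it through.** No arithmetic beyond counting applies, so the check sets the texts side by side.

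**Step 1: every mention of acetaminophen.**

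| Place | Role | Maximum for a subject who starts or escalates after Day 1 |
|---|---|---|
| Synopsis, exclusion 19 | Exclusion, current use | Not stated |
| Section 5.8, item 3 | Exclusion, current use, tied to giving study drug | Not stated |
| Section 6.2, no. 19 | Exclusion, current use | Not stated |
| Section 7.1.2 | Permission during the study | Not stated |

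Four mentions, less three exclusions, less one permission, leaves 4 − 3 − 1 = 0 on-treatment caps.

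**Step 2: whom the exclusion reaches.**

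- Above 3000 mg/day at entry and unable to stop: excluded.
- Above 3000 mg/day at entry and able to stop: may enter, on the footing that the use stops for the whole study. The limit has force during dosing for this subject.
- At or below 3000 mg/day on Day 1, higher later: the current-use condition was not met when eligibility was judged. The Schedule marks the eligibility check on Day 1 only, and no text tells the site to reapply it.

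**Step 3: whether another section closes the third case.** Section 7.5 restricts no medication. Section 8.2.2 does not name exceeding the limit among the reasons for discontinuation. Section 10.3 does not name it among the violations that affect the per-protocol set. By contrast, section 5.8 writes its contraception rule to run "starting from screening through to at least 7 days following the last dose of study medication". The protocol thus has a form of words for a rule that continues through dosing, and does not use it for acetaminophen.

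**Step 4: whether use would be seen.** Over the 10 dosing days the Schedule marks subject reporting of non-prescription medication on 10 of 10 days and study-team assessment on 6 of 10 (Days 1, 3, 5, 7, 9, 10). Section 9.2.2 makes site assessment daily. Sections 9.2.3 to 9.2.5 also require all current medication to be documented at Day 10, at follow-up visits and at early termination. Section 7.5 is narrower. Read strictly, it drops acetaminophen taken for symptoms that are not adverse events. Read leniently, it keeps any new medication but drops a dose increase of an existing one unless taken for an adverse event. Either way it is one sentence against several explicit instructions.

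**The case against.** The strongest reply is that section 5.8 does more than screen. It attaches the limit to giving study drug, sits under safety considerations, and refers to the duration of the study, so the permission in 7.1.2 can reasonably be read as subject to it. This stands in part. A reader might infer that the limit is purely an entry exclusion with no force afterwards, and the documents do not support that: it binds subjects who were above 3000 mg/day at entry. For later starters and escalators, however, the reading has to be supplied by the site.

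Second, investigators can act. Section 5.9.1 ends participation, and section 8.2.2 item 4 allows discontinuation, when a situation is against the subject's interest. Section 9.2.3 repeats AST, ALT and bilirubin at Day 10. These are real safeguards, but discretionary or after the fact, and none sets a dose.

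Third, a reader might infer from 7.5 that non-prescription acetaminophen goes unrecorded. The documents do not support that. Use would be missed only if a site followed 7.5 over 9.2.2 to 9.2.5 and the Schedule. This is a wording inconsistency, not a demonstrated gap in safety data.

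Fourth, no harm is shown. Section 5.8 mentions aminotransferase elevations with favipiravir but calls them mild to moderate, asymptomatic and reversible, and does not link them to acetaminophen. A reader might infer a liver interaction; the documents do not state one. This objection stands and limits the weight of the point.

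Fifth, the cap may already exist elsewhere, since subject instructions and the Manual of Procedures are not among the supplied text. It may also come too late: the amendment history in section 13.0 says versions 4.0 and 5.0 were never implemented and calls version 3.0 the last one implemented. That does not prove that dosing had ended, but it makes the practical benefit uncertain.

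**Conclusion.** The point holds as a minor safety-wording gap. In the supplied text, a subject at or below 3000 mg/day on Day 1 can later exceed the protocol's own threshold without breaching a stated rule, because the limit is framed as current use and 7.1.2 sets no maximum.

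The documents do not say how many subjects would exceed 3000 mg/day, and no number is estimated. Nothing here bears on power, alpha or the comparison between arms.

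The conclusion rests on two assumptions: that no unsupplied subject instruction states the limit, and that some subjects remain to be dosed. If either fails, the practical value falls to little or nothing. The 7.5 recording sentence is secondary and a matter of consistency only.

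**What to change.** In section 7.1.2, add that acetaminophen must not exceed 3000 mg per day through the last dose of study drug, with a cross-reference to section 5.8. Check it at the concomitant-medication reviews already scheduled on Days 1, 3, 5, 7, 9 and 10.

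As secondary tidying, align the recording sentence in 7.5 with 9.2.2 to 9.2.5 and the Schedule, so that all concomitant medication, including non-prescription products, is recorded during dosing.

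The cost is one added sentence, one cross-reference and one corrected sentence. No visits or samples are added. The downside is slightly more questioning at existing contacts. Subjects who need more fever relief keep the NSAID option that 7.1.2 already gives them. The change helps only subjects dosed after it takes effect.

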5.4 Dosing in Special Populations

Favipiravir is contraindicated in nursing mothers and pregnant women or women of child-bearing age who are not taking oral contraception due to its potential teratogenicity. No alteration of dosing is needed in subjects with renal impairment. Total exposure for plasma favipiravir for subjects with severe renal impairment (Stage 4) was 1.3-fold higher compared to subjects with normal renal function. No obvious effect of renal impairment on safety was observed and favipiravir treatment was generally well tolerated in subjects with renal impairment.

No alterations in dosing strategies are required in older adults. The maximum plasma concentration and AUC values in elderly subjects in a single and a multiple-dose study completed in Japan were higher than in young subjects. Comparing AUC values on Day 5, the differences were 40 and 80% after 600 mg once a day and 400 mg BID, respectively. In the companion study completed in the United States of America, there were no differences between young and older populations based on Day 5 AUC comparison in subjects receiving either 600 or 800 mg BID.

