6.0 STUDY POPULATION

6.1 Inclusion Criteria

The study will include subjects with mild-to-moderate COVID-19.³³ Study subjects should meet all of the following criteria:

1. Adults age 18 or older
2. Tested positive for SARS-CoV-2 by RT-PCR or Rapid Antigen assay (first positive test) using a respiratory tract sample (either nasopharyngeal swab OR oropharyngeal swab OR nasal aspirate OR tracheobronchial aspirate OR saliva) collected within 72 hours of randomization
3. Stated willingness to give their written informed consent to participate in the study
4. Stated willingness to comply with all study procedures and availability for the duration of the study
5. Males must be sterile, OR agree not to donate semen AND agree to strictly adhere to contraceptive measures (e.g. condom use) during the study and for 7 days following the last dose of study medication
6. Females must be unable to bear children, OR ensure that their male partner is incapable of fathering a child, OR, if of childbearing potential will strictly adhere to contraceptive measures during the study and for seven days following the last dose of study medication (as detailed in section 5.8)
7. Females must agree to stop breast-feeding prior to first dose of study drug and through seven days after completing therapy
8. Females must have a negative pregnancy test at screening
9. Ability to take oral medication and be willing to adhere to the favipiravir/placebo regimen

10. Minimal baseline severity score for COVID-19-related symptoms: at least two symptoms with a score of 2 or higher. COVID-19-related symptoms include: Stuffy or runny nose, sore throat, shortness of breath, cough, lack of energy or tiredness, muscle or body aches, headache, chills or shivering, feeling hot or feverish, nausea, diarrhea, vomiting. (Excluding changes in the sense of taste or smell).
11. Subject has access to a smart phone, tablet, or PC

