9.4.4 Reporting of Pregnancy

Favipiravir has the potential for teratogenicity. In nonclinical reproductive and developmental toxicity studies, favipiravir was shown to be teratogenic in multiple animal species (mice, rats, rabbits and monkeys). Pregnancy status will be collected at the time of enrollment. Pregnancy testing for women of child bearing potential will occur on study days 1, 7 And 28. Any pregnancy that occurs during study days 1-28 will be followed, until the end, and reported to FDA and other regulatory authorities, where required.

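### Two contraception rules conflict for a drug with stated teratogenic potential: section 5.4 contraindicates women whom section 5.8 and Inclusion 6 admit, and section 5.8 treats a recent vasectomy differently in partners and in male subjects

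*Combined protocol and SAP*

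**What the plan says.** Section 9.4.4 says the drug has potential for teratogenicity and reports that "favipiravir was shown to be teratogenic in multiple animal species (mice, rats, rabbits and monkeys").

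*Women.* Section 5.4 (Dosing in Special Populations) lists as contraindicated, besides pregnant and nursing women, "women of child-bearing age who are not taking oral contraception due to its potential teratogenicity". Section 5.8 (Additional Safety Considerations) takes a wider view. For female subjects of childbearing potential it accepts abstinence, tubal ligation, a copper IUD, condom plus spermicide, a vasectomised partner, or hormonal contraception by the oral, injected, transdermal or implanted route. Inclusion 6, in section 6.1 and in the synopsis, refers to section 5.8 for the detail.

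*Men.* Where the man is a female subject's partner, section 5.8 accepts "Male partner who has had a vasectomy for at least 6 months" and adds "Male partners with vasectomies of <6 months are NOT considered protected". Where the man is himself the subject, the same section says "Men must meet at least one of the following criteria". The list has three items: known sterility, explained as azoospermia; "Underwent vasectomy"; and condom use. The vasectomy item carries no interval.

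Inclusion 5 applies to male subjects as well: "Males must be sterile, OR agree not to donate semen AND agree to strictly adhere to contraceptive measures". It gives no definition of sterile and no reference to section 5.8.

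**The concern.** Contraception is one of the main safeguards in this trial against fetal exposure to a drug with teratogenic findings in animals. If two sections give different answers for the same person, sites may reach different eligibility decisions depending on which section they consult. One site could dose a woman whom another regards as contraindicated. One site could treat a recent vasectomy as sufficient while another asks for more. At stake are fetal safety and uniform eligibility, not the statistical design.

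**Working it through.** No arithmetic applies. The check takes specific people through each rule in the current text; nothing below relies on the amendment history.

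| Person | Section 5.4 | Section 5.8 | Section 6.1 |
|---|---|---|---|
| Woman on oral contraception for 3 months or more, continuing throughout | Not contraindicated on this ground | Accepted | Inclusion 6 met |
| Woman of child-bearing age with a copper IUD, no oral contraceptive | Contraindicated | Accepted | Inclusion 6 met through its reference to 5.8 |
| Woman using an injected, transdermal or implanted hormone for 3 months or more | Contraindicated | Accepted | Inclusion 6 met through its reference to 5.8 |
| Man vasectomised under 6 months ago, as a female subject's partner | No rule | Not counted as protection | Inclusion 6 refers to 5.8 |
| The same man as a subject, not known to be azoospermic | No rule | Meets the list for men | Inclusion 5 unclear |
| Man using condoms and not donating semen for the required period | No rule | Meets the list for men | Inclusion 5 met |

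**Women.** Rows 2 and 3 are a direct contradiction. Section 5.4 makes the oral route the dividing line, whereas section 5.8 treats it as one of four hormonal routes and accepts non-hormonal methods too. Because Inclusion 6 points to section 5.8, its list is operative for entry, so a woman can satisfy every inclusion criterion and still fall under the contraindication.

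**Men, inside section 5.8.** Rows 4 and 5 concern the same man in two roles. The vasectomy item cannot be read as implying proven sterility, because known azoospermia stands beside it as a separate alternative. The section applies an interval in one role and none in the other, and gives no reason for the difference.

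**Men, against Inclusion 5.** A subject must meet all inclusion criteria, so meeting section 5.8 does not release a man from Inclusion 5. If sterile there means azoospermic, as section 5.8 explains the word, a recently vasectomised man not known to be azoospermic must forgo semen donation and use contraception. If vasectomy itself counts as sterility or as a contraceptive measure, he may need less. Inclusion 5 does not settle which.

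**The case against.** The strongest case on the other side is that the eligibility criteria already give sites a route. Section 5.4 is a dosing section, Inclusion 6 sends the reader to section 5.8, and Exclusion 11 asks for effective birth control without requiring an oral method. Section 5.8 also introduces its safety considerations as being for reference. Part of this stands: how often sites would in fact disagree over a copper IUD is unknown. But section 5.4 is still a stated contraindication in the same protocol, and the contraception text in section 5.8 is written as a requirement.

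Four stronger readings are tempting and are not supported:

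- *A recent vasectomy is enough for a man to enter the trial.* It is enough for the section 5.8 list only. Inclusion 5 applies on top, and its effect on him is undefined.
- *Section 5.8 contradicts Inclusion 5 because it omits semen donation.* The two are cumulative. Silence in one does not cancel a condition in the other, and a man who uses condoms and does not donate semen meets both.
- *The contraception window ends on two different days.* Inclusions 5 and 6 refer to the study period and to 7 days after the last dose, while section 5.8 runs "starting from screening through to at least 7 days following the last dose of study medication". With the last dose on Day 10, 10 + 7 gives Day 17, against the end of study on Day 28. But the section 5.8 window covers women only and is a minimum, so continuing to Day 28 satisfies both. Hormonal users must in any case continue throughout the study. This is loose wording.
- *No one can satisfy all the passages at once.* The first and last rows of the table show people who can.

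**Conclusion.** The concern holds for two conflicts. Section 5.4 contradicts section 5.8 and Inclusion 6 for women of child-bearing age who use abstinence or a non-oral method. Section 5.8 is inconsistent on recent vasectomy between partners and male subjects, and Inclusion 5 does not resolve the matter because sterility is undefined there.

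The first conflict potentially reaches all women of child-bearing age in the trial who are not taking oral contraception. The second reaches only men whose vasectomy is less than 6 months old. The documents give neither number. Assuming a share of men among the 1250 subjects would not measure the second group, since the gap does not touch most men.

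The conclusion rests on reading section 5.4 literally and on treating the section 5.8 contraception text as binding, which the reference in Inclusion 6 supports for women. The teratogenicity statement rests on animal data, and the protocol's own term is potential. Power, error control and the planned analyses are not affected. The correction should be made because it is cheap and the safeguard matters.

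**What to change.** Reconcile the synopsis eligibility criteria and sections 5.4, 5.8 and 6.1 so that:

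1. the contraindication in section 5.4 and the method list in section 5.8 agree;
2. the vasectomy provisions for partners and for male subjects are consistent, or the difference is justified in the text;
3. Inclusion 5 cites the reconciled section and defines sterile;
4. the end of the contraception period is stated unambiguously for women and for men.

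Which rule applies in each case is for the sponsor's clinical and safety team to decide; this review does not propose one.

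The cost is wording in the protocol, the consent form and site training, and possibly a few changed eligibility decisions. If enrolment has already closed, the change becomes a written clarification.
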